#### **3.3.4.2 Discontinuation of the trial by the sponsor**

Boehringer Ingelheim reserves the right to discontinue the trial overall or at a particular trial site at any time for any of the following reasons:

1. New toxicological findings or serious adverse events invalidate the earlier positive benefit-risk-assessment. More specifically, the trial will be terminated if more than 50%

Proprietary confidential information © 2018 Boehringer Ingelheim International GmbH or one or more of its affiliated companies

of the subjects show drug-related and clinically relevant adverse events of moderate or severe intensity, or if at least one drug-related serious adverse event is reported.

2. The expected enrolment goals overall or at a particular trial site are not met
3. Violation of GCP, or the CTP, or the contract with BI by a trial site or investigator, disturbing the appropriate conduct of the trial
4. The sponsor decides to discontinue the further development of the investigational product.

The investigator / the trial site will be reimbursed for reasonable expenses incurred in case of trial termination (except in case of the third reason).

### **3.3.5 Replacement of subjects**

In case some subjects do not complete the trial, the trial clinical monitor together with the trial pharmacokineticist and the trial statistician are to decide if and how many subjects will be replaced. A replacement subject will be assigned a unique study subject number.

## **4. TREATMENTS**

### **4.1 TREATMENTS TO BE ADMINISTERED**

The investigational product has been manufactured by BI Pharma GmbH & Co. KG.

#### **4.1.1 Identity of BI investigational product and comparator product**

The characteristics of the test product, dosage and treatment schedule are given below.

Substance: BI 1467335

Pharmaceutical formulation: Film-coated tablet

Source: BI Pharma GmbH & Co. KG, Germany

Unit strength: 5 mg

Posology: 2-0-0

Route of administration: Per os

Duration of use: 28 days

#### **4.1.2 Method of assigning subjects to treatment groups**

This is an open-label trial with one treatment. As all study participants will receive the same treatment, randomisation is not applicable in this trial. The subjects will be assigned to group 1 or group 2 according to the estimated glomerular filtration rate as outlined in [Section 3.3.2](#). At screening the subjects will be allocated to a unique subject identification code. Once a subject is eligible, they will be allocated to a study subject number. Due to the matching criteria, the subjects for the renally impaired Group 1 (eGFR 30 - 59 mL/min/1.73m^2) will be included first in the trial and matched subjects in Group 2 (eGFR ≥90 mL/min/1.73m^2) will be subsequently included.

#### **4.1.3 Selection of doses in the trial**

The dose of 10 mg q.d. selected for this trial reflects the maximum planned therapeutic dose of Phase II studies in NASH patients (see [Section 1.2](#)).

#### **4.1.4 Drug assignment and administration of doses for each subject**

This trial is an open-label study, with a matched-parallel group design. All subjects will receive the same treatment, 10 mg q.d. over 28 days. The inclusion of matched subjects of Group 2 will be done on an individual basis after corresponding renal impaired subjects of Group 1 have completed the treatment period.

If intake of study medication occurs at study site, the trial medication will be administered to the subjects, while in a sitting position, as an oral dose together with about 240 mL of water under supervision of the investigating physician or an authorised designee. The so-called four-eye principle (two-person rule) should be applied for administration of trial medication.

Proprietary confidential information © 2018 Boehringer Ingelheim International GmbH or one or more of its affiliated companies

In case of ambulatory intake subjects are required to contact the site by phone to confirm the intake of study medication.

In principal, for both hospitalized and ambulatory conditions intake of study medication should be performed following an overnight fast, which is to start no later than 10 h before the scheduled dosing. During ambulatory conditions subjects may have breakfast about 1 h after drug intake. If a subject misses his morning dose by 6 h, the subject should omit drug intake on this specific day.

To ensure a dosing interval close to 24 h, the administration or intake (during ambulatory periods) of trial medication should take place at a similar time every day.

Subjects will be kept under close medical surveillance from the evening of Day -1 to the morning of Day 2, from the evening of Day 13 to the morning of Day 15, and from the evening of Day 27 to the morning of Day 29. During the first 2 h after drug administration, subjects should not lie down (i.e. no declination of the upper body of more than 45 degrees from upright posture except for medical examination), or to sleep. For restrictions with regard to diet see [Section 4.2.2.2](#).

#### **4.1.5 Blinding and procedures for unblinding**

This Phase I trial will be handled in an open fashion throughout (i.e. during the conduct, including data cleaning and preparation of the analysis). This is considered acceptable because the potential for bias seems to be low and does not outweigh practical considerations.

Emergency envelopes will not be provided, since all subjects receive the same dose and study is an open label design.

#### **4.1.6 Packaging, labelling, and re-supply**

Drug supplies will be provided by the Department of Pharmaceutical Development of Boehringer Ingelheim Pharma GmbH & Co. KG, Biberach, Germany.

The clinical trial supply consists of containers holding the trial medication which are labelled with trial identification. Each subject receives on a weekly basis one small box which contains two blisters. The subject number, study week, dispensing date and name of investigator need to be written in the corresponding empty fields on the box label. On the blister labels the subject number need to be included as well.

The required information according to the German Drug Law as well as Annex 13/EU GMP Guideline will be provided on the small boxes and they will be labelled with:

- BI trial number
- Name of product and strengths or identification code
- Pharmaceutical dosage form, quantity of dosage units
- Route and mode of administration
- Term 'For Clinical Trial Use' (domestic language)
- Sponsor name and address
- Storage conditions
- Use-by date

- Placeholder to include Subject number
- Batch number
- Tick box to include study week
- Placeholder to include dispensing date
- Placeholder to include name of investigator

The telephone number of the sponsor and name, address and telephone number of the trial site are given in the subject information form. The EudraCT number is indicated on the title page of this protocol as well as on the subject information and informed consent forms.

Examples of the labels will be available in the ISF.

Re-supply may be required.

#### **4.1.7 Storage conditions**

Drug supplies will be kept in their original packaging and in a secure limited access storage area according to the recommended storage conditions. Where necessary, a temperature log must be maintained to make certain that the drug supplies are stored at the correct temperature. This applies only to the investigational site and not for storage conditions at subjects home. If the storage conditions at the investigational site are found to be outside the specified range, the local clinical monitor (as provided in the list of contacts) is to be immediately contacted.

#### **4.1.8 Drug accountability**

The investigator / pharmacist / investigational drug storage manager will receive the investigational drugs delivered by the sponsor when the following requirements are fulfilled:

- Approval of the trial protocol by the IRB / ethics committee
- Availability of a signed and dated clinical trial contract between the sponsor and the head of the trial site
- Approval/notification of the regulatory authority, e.g. competent authority
- Availability of the curriculum vitae of the principal investigator
- Availability of a signed and dated clinical trial protocol
- Availability of the Form 1572

Only authorised personnel as documented in the form 'Trial Staff List' may dispense medication to trial subjects. The trial medication must be administered in the manner specified in the CTP. All unused medication will be disposed locally by the trial site upon written authorisation by the clinical monitor. Receipt, usage and disposal must be documented on the respective forms. Account must be given for any discrepancies.

The investigator / pharmacist / investigational drug storage manager must maintain records of the product's delivery to the trial site, the inventory at the site, the use by each subject, and the disposal of unused products.

Proprietary confidential information © 2018 Boehringer Ingelheim International GmbH or one or more of its affiliated companies

These records will include dates, quantities, batch / serial numbers, expiry ('use-by') dates, and the unique code numbers assigned to the investigational products and trial subjects. The investigator / pharmacist will maintain records that document adequately that the subjects were provided the doses specified by the CTP, and that reconcile all investigational products received from the sponsor. At the time of disposal, the investigator / pharmacist must verify that all unused or partially used drug supplies have been returned by the clinical trial subject and that no remaining supplies are in the investigator's possession.

## **4.2 OTHER TREATMENTS, EMERGENCY PROCEDURES, RESTRICTIONS**

### **4.2.1 Other treatments and emergency procedures**

There are no special emergency procedures to be followed. No additional treatment is planned. However, in case of adverse events in need of treatment, the investigator can authorise symptomatic therapy. In those cases, subjects will be treated as necessary and, if required, kept under supervision at the trial site or transferred to a hospital until all medical evaluation results have returned to an acceptable level.

### **4.2.2 Restrictions**

#### **4.2.2.1 Restrictions regarding concomitant treatment**

In healthy subjects, no concomitant therapy is allowed except for hormonal contraceptives or ovary hormone replacement. All concomitant or rescue therapies will be recorded (including time of intake on study days) on the appropriate pages of the CRF.

Concomitant medication is allowed for treatment of concomitant or underlying disease in subjects with renal impairment (group 1). A case-by-case decision may be made after consultation with the sponsor if drug-drug interactions are likely to occur.

Since BI 1467335 demonstrated *in vitro* to be an irreversible inhibitor of monoamine oxidase B (MAO-B), patients should be advised to avoid medications that interact with MAO-B inhibitors. These include for example medications prohibited 2 weeks prior to BI 1467335 dosing and during study participation (Meperidine, Tramadol, Methadone, Propoxyphene, Dextromethorphan, Cyclobenzaprine, Sympathomimetic medications including nasal, oral and ophthalmic decongestants and cold remedies) and medications prohibited 5 weeks prior to BI 1467335 dosing, during study participation, and up to 14 days after last intake of BI 1467335, such as MAO Inhibitors and antidepressants (SSRIs, SNRIs, triazolopyridine, tricyclic or tetracyclic antidepressants).

Any newly introduced medication should be only used after consultation and approval of the medical investigator.

In the case of AEs the volunteers will be treated as necessary and kept under constant supervision at the trial centre or transferred to hospital until such time that all the results of the evaluations have returned to a medically acceptable level.

#### **4.2.2.2      Restrictions on diet and life style**

All subjects should be requested to refrain from meat (and creatin containing products used for bodybuilding) for at least 12 hours before blood sampling for serum creatinine is to be done. All subjects should refrain from heavy exercise for 24 hours before blood sampling for serum creatinine is to be done.

While admitted to the trial site the subjects are restricted from consuming any other foods or drinks than those provided by the staff. Standardised meals will be served at the time points described in the [Flow Chart](#).

On Day 1, Day 14 and Day 28, fluid intake from breakfast until 22 hours post-dose should be within about 1000 to 3000 mL.

Alcoholic beverages, grapefruits, Seville oranges (sour or bitter oranges) and their juices, and dietary supplements and products including St. John's wort (*Hypericum perforatum*) are not permitted starting 7 days before the first administration of trial medication until after the last PK sample is collected.

Methylxanthine-containing drinks or foods (such as coffee, tea, cola, energy drinks, and chocolate) are not allowed at days of inhouse confinement.

Patients should be advised to avoid foods containing a very large amount of tyramine (especially found in fermented food) while taking BI 1467335. These include for example aged cheese, aged meats, soybean products (soy sauce), red wine, tap (draft) beer, St John's Wort, pickled herring, sauerkraut (fermented cabbage), and tryptophan supplements.

Excessive physical activity (such as competitive sport) should be avoided starting 7 days before the first administration of trial medication until the end of trial examination.

If female subjects of child bearing potential are included, adequate contraception, double barrier method, is to be maintained throughout the course of the trial (see [Section 3.3.2](#) for adequate measures).

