7. Safety laboratory, ECG, blood pressure assessment and AE questioning to be done and medically evaluated within 3 days prior to first administration of study drug; this visit can be omitted, if the screening examination is performed on Days -5, -4 or -3.
8. At End of Trial Examination the time of 9999:00 is only a dummy time for PK sampling.
9. A blank urine sample (x) is to be obtained prior to the administration of trial medication on Day 1. On Day 1, 14 and 28 fractionated urine sampling 0-4, 4-8, 8-12, and 12-24 h will be conducted.
10. Administration under fasting conditions.
11. Includes a blood sample for pharmacogenetic analysis.
12. Samples to be drawn immediately (within 30 minutes) prior to drug administration.
13. On Day 1, 2, 4, 7, 10, 14, 15, 17, 21, 25, 26 and 28 dose to be taken at study site.
14. Confirmation of fitness includes physical examination.
15. On Day 3, Days 5 to 6, Days 8 to 9, Days 11 to 13, Day 16, Days 18 to 20, Days 22 to 24 and Day 27 subjects are allowed to take their study medication at home if deemed appropriate by the investigator. Compliance of medication intake will be monitored by phone call.

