BI 1467335 inhibited MAO-B catalyzed kynuramine deamination with an IC50 of 1.04  $\mu\text{M}$  and MAO-A catalyzed kynuramine deamination with an IC50 of 74.4  $\mu\text{M}$  ([n00257993](#)). Time dependent inhibition of MAO-B catalyzed kynuramine deamination by BI 1467335 was observed indicating an irreversible inhibition mechanism. Inhibition constants for irreversible enzyme inhibition were determined and resulted in an inhibition constant (Ki) of 2.01  $\mu\text{M}$  and an inactivation rate constant (kinact) of 0.087  $\text{min}^{-1}$  ([n00259383](#)).

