Description of change	Section 1.2: Implementation of new in vitro data classifying BI 1467335 as potential irreversible MAO-B inhibitor. Section 4.2.2: Addition of prohibited foods and drugs to mitigate the risk of relevant adverse reactions.
Rationale for change	Time dependent inhibition of MAO-B catalyzed kynuramine deamination by BI 1467335 was observed indicating an irreversible inhibition mechanism.

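### The tyramine advice stops with the last dose on Day 28, although it rests on irreversible in vitro MAO-B inhibition and the residual effect period is not known; extending it to the end of trial visit would be a cheap precaution.

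*Protocol*

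**What the plan says.** **Food advice.** Section 4.2.2.2 of the protocol reads: "Patients should be advised to avoid foods containing a very large amount of tyramine (especially found in fermented food) while taking BI 1467335". It then gives nine items as examples. No other sentence extends this advice beyond dosing.

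**Origin.** Amendment 2 (Section 11) describes the change to Section 4.2.2 as "Addition of prohibited foods and drugs to mitigate the risk of relevant adverse reactions". Foods and drugs were added together under one rationale, which Section 1.2 also reports: "Time dependent inhibition of MAO-B catalyzed kynuramine deamination by BI 1467335 was observed indicating an irreversible inhibition mechanism".

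**Drug rules from the same amendment (Section 4.2.2.1).** One list covers "medications prohibited 2 weeks prior to BI 1467335 dosing and during study participation". The other, MAO inhibitors and antidepressants, is prohibited from 5 weeks before dosing, "during study participation, and up to 14 days after last intake of BI 1467335".

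**Neighbouring rules in Section 4.2.2.2.** Alcohol, St John's wort and dietary supplements "are not permitted starting 7 days before the first administration of trial medication until after the last PK sample is collected". Excessive physical activity "should be avoided starting 7 days before the first administration of trial medication until the end of trial examination". Meat is to be avoided for at least 12 h before each serum creatinine sample. While in house, subjects eat only what staff provide.

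**Residual effect.** Section 5.2.2.2 states that the period after the last dose in which drug levels or pharmacodynamic effects are likely to persist is not known. It therefore counts all adverse events up to the end of trial examination as on treatment.

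**The concern.** If an enzyme is inhibited irreversibly, the inhibition can outlast the last tablet. Advice tied to tablet intake then ends at a point that the stated mechanism does not support. The drug rules adopted for the same reason do not end there, and the adverse event rules treat the period up to the end of trial visit as still on treatment.

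What is at stake is subject safety during the days between discharge and the end of trial visit, when subjects are at home and choose their own food. The restriction was added to reduce the risk of adverse reactions, and for most of the listed foods it lapses once staff-controlled meals end. The pharmacokinetic endpoints are not involved.

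**Working it through.** The plan gives no figure to reproduce. The check is day arithmetic from the Flow Chart and a comparison of rules.

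**Timing.** Inputs from the Flow Chart: last dose at 648 h, discharge at 673 h, ambulatory visits at 696, 720, 768 and 816 h, end of trial visit on Day 38 to 41. The end of trial visit is taken at 08:00, so its time is (Day − 1) × 24 h.

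- Last dose: 648 / 24 + 1 = Day 28.
- Discharge: 673 − 648 = 25 h after the last dose, on the morning of Day 29. Staff-provided food ends here.
- End of trial visit: Day 38 = 37 × 24 = 888 h; Day 41 = 40 × 24 = 960 h.
- From discharge to that visit: 888 − 673 = 215 h (9.0 days) to 960 − 673 = 287 h (12.0 days).
- From the last dose to that visit: 888 − 648 = 240 h (10 days) to 960 − 648 = 312 h (13 days).
- Fourteen days after last intake: 648 + 336 = 984 h, which is Day 42.
- Ambulatory visits inside the gap: Days 30, 31, 33 and 35, that is 48, 72, 120 and 168 h after the last dose.

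**Coverage after Day 29.** Each example item was set against the other rules in Section 4.2.2.2.

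| Item | Other rule after Day 29 |
|---|---|
| Red wine | Alcohol ban |
| Draft beer | Alcohol ban |
| St John's wort | Named in the supplement ban |
| Tryptophan supplements | Supplement ban |
| Aged meats | Only the 12 h no-meat rule before creatinine sampling |
| Aged cheese | None |
| Pickled herring | None |
| Sauerkraut | None |
| Soybean products | None |

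So 9 − 4 = 5 items have no tyramine-specific advice, and 4 of those 5 have no rule of any kind. The alcohol and supplement ban ends with the last PK sample. Footnote 8 of the Flow Chart places a sample at the final visit: "At End of Trial Examination the time of 9999:00 is only a dummy time for PK sampling". The ban therefore runs to Day 38 to 41.

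**End points side by side.**

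| Rule | Ends |
|---|---|
| Tyramine advice | Day 28 |
| Alcohol and supplement ban | Last PK sample, Day 38 to 41 |
| Exercise rule | End of trial visit, Day 38 to 41 |
| First drug list | End of study participation (undefined; most naturally Day 38 to 41) |
| MAO inhibitors and antidepressants | Day 42 |

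**What is known about the risk.** Section 1.2 gives an IC50 of 1.04 µM for MAO-B and 74.4 µM for MAO-A, a ratio of 74.4 / 1.04 = 71.5. Irreversible inhibition is reported for MAO-B only, and in vitro only. The documents give no enzyme recovery time and no tyramine-response data.

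**The case against.** The strongest reply is that the food window is a deliberate choice. Its wording is explicit, and a shared rationale does not require a shared duration. The two drug lists already differ from each other: 2 against 5 weeks before dosing, and study participation against 14 days afterwards. The pre-dose periods cannot reflect persistence of BI 1467335, so at least that part of each window follows the co-medication. The protocol gives no reason for the length of any window, so the lack of one here is not a distinguishing fault. All of this stands. A reader might infer that the food and drug rules contradict each other; the documents do not support that.

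The second reply is that no hazard has been shown. This also stands. The MAO-A IC50 is about 72-fold higher than that for MAO-B, and the recovery of MAO-B is not described. Amendment 2 is marked for immediate implementation to eliminate hazard, from which a reader might infer a demonstrated risk after the last dose. That marking applies to the amendment as a whole and says nothing about the days after Day 28. The unknown residual effect period shows uncertainty, not harm.

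Smaller points also stand. The nine items are examples, so five of nine does not measure exposure. What subjects are actually told cannot be checked, because the subject information was not available for this review. The visits on Days 30, 31, 33 and 35 include questioning for adverse events, which limits unobserved risk.

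None of these points is a reason for ending the advice at the last dose, and no other section closes the gap. The protocol does not use MAO-B selectivity to justify the shorter period.

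**Conclusion.** The point holds as a low-cost precaution. The tyramine advice ends on Day 28, while its stated basis is a mechanism that can outlast dosing and the residual effect period is declared unknown. Five of the nine example items then carry no tyramine-specific advice for about 9 to 12 days between discharge and the end of trial visit.

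Two readings underlie these figures: that the last PK sample is the one at the end of trial visit, and that study participation, which the protocol does not define, lasts to that visit. Only the 14-day rule for MAO inhibitors and antidepressants states its post-dose duration in days. A reader might infer that the foods must follow that rule to Day 42. The documents do not support this, because the protocol does not apply the 14 days even to the first drug list.

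The size of the risk cannot be derived from the documents.

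**What to change.** In Section 4.2.2.2, let the tyramine advice apply *while taking BI 1467335 and until the end of trial examination*. This gives it the same end point as the exercise rule in that section. Remind subjects at the Day 29 discharge and at the existing visits on Days 30, 31, 33 and 35.

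The cost is one sentence in an amendment and, if it does not already say so, in the subject information. No visits are added. Each subject follows the diet advice for 10 to 13 more days, counted from the last dose.

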#### *Toxicology*

The NOAEL in rats orally exposed to BI 1467335 for 13 weeks was 12.5 mg/kg. This dose corresponded to mean C(max) and AUC(0-24h) levels of 8430 nM and 65700 nM.h, respectively, in rat. The NOAEL in dogs orally exposed to BI 1467335 for 13 weeks was 3 mg/kg. This dose corresponded to mean Cmax and AUC(0-24h) levels of 3000 nM and 25900 nM.h, respectively, taken from the sex with the lower plasma exposure at the NOAEL. This provides an adequate safety window between clinical exposure and exposure at NOAEL levels in animals. For further details, please refer to the current 'Investigator's Brochure (IB)' [[c04751792](#)].

These findings are consistent with results of the 4 weeks toxicology studies in rats and dogs [[n00244592](#)] [[n00247850](#)].

BI 1467335 does not present a genotoxic hazard.

In the study on embryo-fetal development in rabbits with BI 1467335 treatment from day 6-18 of gestation, abortion was noted in one doe treated at 10 mg/kg (with marked maternal toxicity) and in three does at 45 mg/kg. Due to these findings Women of childbearing potential must be willing and able to use a double-barrier contraception (barrier in the meaning of method) with at least one highly effective method of birth control per ICH M3 (R2) that result in a low failure rate of less than 1% per year when used consistently and correctly in this study (1386-0002).

The pharmacokinetic behavior of BI 1467335 in rats and dogs was characterised by rapid absorption, a low to moderate half-life and a predominantly over proportional increase of

Proprietary confidential information © 2018 Boehringer Ingelheim International GmbH or one or more of its affiliated companies

plasma exposure with an increase in dose. The in vitro plasma protein binding was low in all investigated species, with  $\leq 25\%$  bound in human plasma. In vitro studies in cryopreserved human hepatocytes indicated a prevalence of oxidative O-dealkylation as primary metabolic pathway.

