### **3.3.2 Inclusion criteria**

Subjects will only be included into the trial, if they meet the following criteria:

1. Despite of moderate renal impairment (Group 1) healthy male or female subjects according to the assessment of the investigator, based on a complete medical history including a physical examination, vital signs (BP, PR), 12-lead ECG, and clinical laboratory tests
2. eGFR based on CKD-EPI formula for Group 1 between 30 and 59 mL/min/1.73m^2 and for Group 2  $\geq 90$  mL/min/1.73m^2
3. Age of 18 to 79 years (incl.)
4. BMI of 18.5 to 34 kg/m^2 (incl.)
5. Signed and dated written informed consent prior to admission to the study in accordance with GCP and local legislation
6. Male subjects, or female subjects who meet any of the following criteria (according to the CTFG Recommendations related to contraception and pregnancy testing in clinical trials, methods with a failure rate of less than 1% per year) starting from at least 30 days before the first administration of trial medication and until 30 days after trial completion, e.g.:
  - Use of adequate contraception, e.g. any of the following methods *plus* condom: implants, injectables, combined oral or vaginal contraceptives (inhibition of ovulation)
  - Hormonal intrauterine device
  - Sexually abstinent (defined as refraining from heterosexual intercourse during the entire period of risk)
  - A vasectomised sexual partner (provided that vasectomy was performed at least 1 year prior to enrolment and the vasectomised partner has received medical assessment of the surgical success)
  - Surgically sterilised (including bilateral tubal occlusion, hysterectomy)

Proprietary confidential information © 2018 Boehringer Ingelheim International GmbH or one or more of its affiliated companies

- Postmenopausal, defined as at least 1 year of spontaneous amenorrhea (in questionable cases a blood sample with simultaneous levels of FSH above 40 U/L and estradiol below 30 ng/L is confirmatory)

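### Inclusion criterion 6 accepts a hormonal intrauterine device or a vasectomised partner alone, while Sections 1.2 and 4.2.2.2 require two contraceptive methods (minor)

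*Protocol*

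**What the plan says.** Three parts of the current protocol text deal with contraception in female subjects.

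- **Section 1.2, Toxicology.** After reporting abortions in the rabbit embryo-fetal study (one doe at 10 mg/kg, with marked maternal toxicity, and three at 45 mg/kg), it sets a rule for women who could become pregnant: each "must be willing and able to use a double-barrier contraception (barrier in the meaning of method) with at least one highly effective method". The sentence closes by tying the rule to this trial by number: "less than 1% per year when used consistently and correctly in this study (1386-0002").
- **Section 4.2.2.2, Restrictions on diet and life style.** If such women are included, "adequate contraception, double barrier method, is to be maintained throughout the course of the trial". It points to Section 3.3.2 for the adequate measures.
- **Section 3.3.2, inclusion criterion 6.** It admits male subjects, or "female subjects who meet any of the following criteria", under a general standard of "methods with a failure rate of less than 1% per year". The first item pairs each listed contraceptive with a "condom: implants, injectables, combined oral or vaginal contraceptives (inhibition of ovulation"). Separate items then read "Hormonal intrauterine device" and "A vasectomised sexual partner (provided that vasectomy was performed at least 1 year prior to enrolment", with medical confirmation of success). The remaining items are abstinence, surgical sterilisation and postmenopausal status.

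**The concern.** Section 1.2 says that barrier is to be read as method, so its rule is two methods, one of them highly effective. Criterion 6 is satisfied by one item, and the device and vasectomised-partner items mention no second method. A woman relying on either alone passes the entry check and does not meet Sections 1.2 and 4.2.2.2.

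The stakes are practical. A site applying criterion 6 correctly could enrol a woman who is then in breach of a trial restriction, and Section 4.3 allows a subject who violates restrictions to be removed. Section 3.3.2, the section a site uses to decide eligibility and to counsel on acceptable methods, does not tell it that these two items need something more.

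**Working it through.** No statistical quantity is involved, so the check is a comparison of the texts and a count of the items.

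**Step 1: apply each rule to each item of criterion 6.**

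| Item in criterion 6 | Childbearing potential? | Second method stated? | Meets the two-method rule as listed? |
|---|---|---|---|
| Implant, injectable, combined oral or vaginal contraceptive | Yes | Yes, condom | Yes |
| Hormonal intrauterine device | Yes | No | No |
| Sexual abstinence | Yes | Not needed | No exposure to guard against, but not stated |
| Vasectomised partner | Yes | No | No |
| Surgically sterilised | No | Not applicable | Rule does not apply |
| Postmenopausal | No | Not applicable | Rule does not apply |

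Count: 6 items − 2 that do not concern childbearing potential = 4. Of these 4, 1 states a second method, 1 needs none, and 4 − 1 − 1 = 2 state none.

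**Step 2: allow for the layout.** The first item introduces a list of methods that each need a condom. If the device item was nested under it in the original layout, the count falls to 2 − 1 = 1 of 4. As the text reads, the device is a separate item. The vasectomised-partner item conflicts on either reading.

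**Step 3: look for text elsewhere that supplies the missing method.**

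- Exclusion criterion 31 requires a condom or abstinence, but of male trial subjects with a partner of childbearing potential. It does not cover partners of female subjects.
- Section 3.3.3 ends by sending the reader to Section 4.2.2 for restrictions. Section 4.2.2.2 sends the reader back to Section 3.3.2, where the second method is missing for these items. The two references form a loop and do not say which rule prevails.
- Section 1.2 does not defer to Section 3.3.2.

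**Step 4: check the term itself.** Section 4.2.2.2 uses the double-barrier term without the definition given in Section 1.2. Read literally, as two barrier methods, it would not match even the first item, which pairs a hormonal method with a condom.

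**Step 5: list the safeguards that remain.** The standard of under 1% failure per year applies to the whole of criterion 6. Section 5.2.3 schedules pregnancy tests at screening (1), on Days -1, 13 and 27 (3) and at end of trial (1): 1 + 3 + 1 = 5. Section 3.3.4.1 stops trial medication immediately in pregnancy.

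**The case against.** The strongest reply is that the rules are cumulative. Criterion 6 governs entry and Section 4.2.2.2 governs conduct, and a woman with a device or a vasectomised partner satisfies both by adding a condom. The eligibility section does refer the site to Section 4.2.2. This stands in part: such a woman is still bound by the restriction and breaches it only if she adds nothing. It does not settle the matter, because a site following the reference is sent back to a list that presents the two items as sufficient.

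A second reply is that Section 4.2.2.2 defers to Section 3.3.2 for what is adequate, that its double-barrier phrase is loose shorthand, and that Section 1.2 is background. That would carry more weight if Section 1.2 did not state its rule as mandatory and name this trial.

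Third, Section 11 shows that Amendment 1 was the one that dealt with contraception, and it changed only Section 3.3.2. Amendment 2 reopened Sections 1.2 and 4.2.2 for monoamine oxidase B data and prohibited foods and drugs. The sponsor's latest deliberate contraception text may therefore be criterion 6. This bears on which rule the sponsor intends. It does not make the current sections agree.

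Finally, the device half of the point depends on layout, and the practical consequence is slight. Both are accepted.

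**Conclusion.** The inconsistency is real and is in current text: the entry rule accepts less than the protocol's own mandatory rule requires. It affects 2 of the 4 items relevant to women of childbearing potential as the list reads, or 1 of 4 if the device item belongs under the condom requirement.

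It is minor. How many women would be affected is not stated and may be none, since Section 4.2.2.2 itself is conditional on such women being included. Those affected would still use a method with under 1% annual failure, and removal for a breach is discretionary. No endpoint, analysis set or PK comparison changes.

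The conclusion rests on reading Section 1.2 as a two-method rule, which its own gloss supports, and on taking the criterion's wording at face value, so that any one item is enough.

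**What to change.** Choose one rule and state it in every section.

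**Preferred, because Section 1.2 makes two methods mandatory for this trial:**

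- In criterion 6, add a second method, such as a condom, to the hormonal intrauterine device and vasectomised-partner items.
- In the same place, state that true abstinence satisfies the rule.
- In Section 4.2.2.2, replace the double-barrier term with wording such as *two methods, at least one highly effective, as listed in Section 3.3.2*.

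**Alternative:** if the sponsor intends one highly effective method to be enough, amend Sections 1.2 and 4.2.2.2 to say so and leave criterion 6 as it is.

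Either way, the cost is a wording amendment to two sections (3.3.2 and 4.2.2.2, or 1.2 and 4.2.2.2) and the matching subject-information text. Keeping two methods makes entry slightly stricter for women using one of the two items. Neither route affects the PK comparison.
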